6. DETAILED RESEARCH PLAN

METHODOLOGY

I. Study Design

The study will be a prospective longitudinal cohort study, which will monitor the diagnosis, treatment and follow-up of the HIV patients identified with a chronic hepatitis C within 3 clinic sites in Manipur; Churachandpur, Chakpikarong and Moreh.

The analysis of routinely collected clinical data will facilitate the assessment of the effectiveness of HCV treatment among patients with chronic hepatitis C, co-infected with HIV, from time of confirmation of their HCV Viral load until SVR12, death, lost to follow up, medical decision to exit the study or transfer out, whichever comes first.

The study will assess implementation of new recommended HCV-curative regimens in real world settings, not specific new drugs. The specific treatment regimens used, including new DAAs, will be selected in accordance with current WHO, international and national recommendations and protocols (18-20). Of the new DAA's, only drugs registered and available in India will be used in accordance with international and national recommendations and protocols.

II. Study population

The study population will include HIV infected patients from Manipur state diagnosed with chronic hepatitis C (viral load HCV positive) meeting eligibility criteria. These patients will be directly identified in the MSF sites.

III. Sample size

The sample will exhaustively include all patients meeting the inclusion criteria in each site for a period of two years. Currently MSF, in collaboration with NACO has approximately 1600 adult patients being actively followed up for HIV care within Manipur. The overall rate of HIV-HCV co-infection, based on HCV serological screening performed to date is approximately 27%. Assuming 80% of serologically positive patients have chronic hepatitis C, the minimum sample size expected for this study will be 345 patients.

IV. Sampling design

The sample will exhaustively include all patients meeting the inclusion criteria in each site for a period of two years.

Inclusion and Exclusion criteria:

When the results of VL tests become available, all patients over 18 years will be invited to participate in the study, if they fulfill eligibility criteria. Inclusion is not linked with eligibility for HCV or HIV *treatment*. A criterion of non-eligibility to treatment is not considered as inclusion or exclusion criteria for study participation¹.

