The individual may withdraw consent at any point during the study with no impact on treatment and care.

¹ Eligibility for study inclusion and HCV treatment are different. The study will also include HCV positive patients who do not receive treatment either due to non-priority of treatment or presence of clinical contraindications. (These patients may receive treatment at a later date). This is intended to fulfil secondary objectives 'i' and 'j'. However patients will receive standard HCV treatment and care in the event of non-eligibility to the study or refusal to participation in the study.

Table 1: Study participant eligibility criteria

	Eligibility criteria for study inclusion	Eligibility criteria for HCV treatment
Inclusion criteria	
 • HIV/HCV co infection independent of the stage of liver disease • Over 18 years of age • HCV viral load greater than 12UI/mL • HIV positive status confirmed by the national and MSF algorithm • Able and willing to provide informed consent • Willing to comply with all study procedures 	Clinical Review 
 • Confirmed HCV infection • HIV infection controlled on ART or asymptomatic HIV infection with CD4 count >500/ μL in the absence of ART • Controlled drug use • Controlled opportunistic infections • Hemoglobin threshold: 9 g/dL
		Psychosocial Review 
 • Adherent to HIV treatment and appointments • Controlled use of substances (if relevant) • No evidence of uncontrolled psychiatric disorder
Exclusion criteria	
 • Individual aged less than 18 years • Individual does not consent to be part of the study. 	Clinical Review 
 • Evidence of hepatocarcinoma • Advanced/terminal heart or pulmonary or renal or other disease • Active, uncontrolled opportunistic Infections • First 3 months of a new ART regimen (unless minor ARV change for toxicity); • Pregnancy or planning pregnancy in following months, unwillingness to use contraception Breastfeeding women.
		Psychosocial Review 
 • Unwillingness of the patient to adhere to HCV treatment & ART • Uncontrolled severe psychiatric disorder. • Unstable substance use

V. Statistical methods to be used

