Question 21 on CRF1 (Appendix 2) will identify patients who have consented to be part of the cohort study.

21_Did the patient sign an informed consent for the cohort study Yes No DK

In the event of a serious adverse event occurring, the Indian national "Suspected Adverse Drug Reaction Reporting Form" will be completed. This can be found at the following web link:

<http://www.ipc.gov.in/PvPI/ADRReportingForm.pdf>

VII. Implementation / Operational Plan

As outlined within the introduction, MSF has been active in Manipur since 2004 and now has ART centres in Churachandpur, Chakpikarong and Moreh providing care and treatment for over 1600 patients living with HIV/AIDS (PLWHA). As part of MSF's commitment to provide high quality care to PLWHA, treatment of HCV for HIV co-infected individuals was commenced in 2015. As such, the treatment activities, on which this prospective observational study will be based, are a part of MSF's on-going routine operational activities.

The following describes these current operational activities in addition to supplementary activities which will be incorporated for the conduct of a scientifically rigorous prospective observational study.

Participant's recruitment

Serological screening for HCV has been routinely undertaken on all confirmed HIV positive patients entering within the MSF facility since 2012. Serological rapid tests, approved by Indian regulatory authorities have been used for this purpose. During 2015 confirmation of active HCV infection was commenced within the program with Real time PCR for virology on a Roche platform within Babina private laboratory, Imphal.

Patients with a HCV viral load detectable and a co-infection with HIV will be proposed to join the study, if they fulfil eligibility criteria for the study. Patients eligible to participate in the study will receive comprehensive information about the treatment regimen and the study, its risks and benefits, the study's objectives and procedures.

In addition to the verbal information, a Patient Information Sheet concerning the study will be provided, with contact information (Appendix 5).

For individuals who are eligible and interested in participating, the health staff will obtain informed consent from the individual to participate to the study (Appendix 5) Consent form and Patient Information Sheets will be translated and back translated in the local languages most adapted to the patients, where possible.

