The following definitions will be considered:

In case of viral load detectable 12 weeks after end of treatment, the outcome will be considered as treatment failure.

- Deaths will be recorded by the medical teams, notified by a close relative or friend or reported by a tracing team (for programs implementing such strategy).
- Loss to follow-up is defined as two months after a planned date of appointment without contact, among patients who were not dead or transferred out.
- Transfer out is defined as a patient who has been transferred to another medical facility or consultation and for whom the treatment outcome is not known, without the possibility to continue the HCV follow up in the study site. Patients that require to be transferred out will be informed that it is very unlikely that they can continue HCV treatment. In case of possible return to the study site, the patient may be proposed again to enter in the study and informed consent will be sought again. The same identification number will be used.
- Exit due to medical reason is defined as a cessation of follow decided by the clinicians, in collaboration with the patients, due to other more urgent medical needs.

Secondary endpoints:

- Proportion of patients included in the cohort by socio-demographic characteristics: age group, sex, occupation, marital status, risk factors of HCV exposition

- Proportion of patients included in the cohort by clinical and biological characteristics: genotype, HCV viral load, liver fibrosis staging, presence of ascites, HIV WHO staging at baseline, CD4 count and HIV viral load prior to HCV treatment, HBV status, Child pugh score, hematology, biochemistry
- Proportion of patients with HBV infection defined as a positive RDT with HBV AgS diagnosis
- Distribution of liver fibrosis stage among included population
- Proportion of patients with HCV treatment initiated
- Proportion of SVR 12 among the patients having completed HCV treatment.
- Proportion of patients with SVR 12 stratified by regimen and by genotype
- Proportion of patients with SVR 12 stratified by site
- Mortality among the patients in the HCV cohort overall, and among patients who initiated treatment or among patients without treatment initiation
- Proportion of defaulters during before, during and after treatment
- Proportion of patients transferred out, and for whom medical decision to interrupt HCV follow up has been taken

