- Frequency and type of demographic, clinical and biological risk factors associated with treatment outcomes: age , sex, liver fibrosis stage, child pugh score, genotype, clinical symptoms, comorbidities with HBV infection , addiction
- Concerning the safety of HCV treatment: Frequency and type of treatment-related side effects or events that cause modification of dosage of the HCV treatment
- Frequency and type of treatment-related side effects that cause permanent interruption (discontinuation) of the HCV treatment
- Concerning the feasibility of HCV treatment: Proportion of patients included in the cohort but non eligible to treatment at the first assessment, by clinical and biological characteristics, over time (yearly eligibility assessment): HCV viral load, liver fibrosis stage, child pugh score, presence of ascites,HIV viral load
- Frequency and type of demographic, clinical and biological risk factors associated with non-eligibility to treatment: age , sex, fibrosis stage, child pugh score, genotype, clinical symptoms, biological anomalies, comorbidities with HBV infection, addiction
- Frequency of reporting of missed doses by patients

IX. Data management

Data Collection Tools

Paper based questionnaires and lab forms will be used for collection of individual baseline information, clinical evaluation information, laboratory results and treatment information. The different CRFs are presented in Appendix 1 and 2. Other data collection tools may be used in the laboratory. Questionnaires will be pre-tested prior to initiation of data collection. Study forms will be linked through unique study numbers assigned to study participants. Personal identifier information will be recorded on separate forms, and will be kept separately to maintain confidentiality.

Listing of data collection questionnaire (Appendix 1 & 2):

- Baseline information
- Consultation form
- Comorbidities form
- Biological form

- Adverse Events form

In case of adverse events, specific reports will be filled, initial and follow up reports (Appendix 3).

Prior to the inclusion in this cohort, the patient may be under medical follow up for his HIV and / or HCV care. These data are collected on different tools. Some information would be used for this study. As example, the CD4 count at enrolment will be found in the HIV database used in the HIV care facility. The source of the data is specific to each site. The data will be reported to the HCV database.

Data Management and Monitoring

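### Mortality split by ever-treated status, on a clock that starts at viral-load confirmation, favours the treated group even when death rates are equal

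*Protocol*

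**What the plan says.** The secondary endpoints in section 6.VIII (Study Outcome Measures) include "Mortality among the patients in the HCV cohort overall, and among patients who initiated treatment or among patients without treatment initiation". The bullet classifies patients, not person-time, and does not say whether mortality means a proportion or a rate.

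The study window in section 6.I (Study Design) runs "from time of confirmation of their HCV Viral load until SVR12, death, lost to follow up, medical decision to exit the study or transfer out".

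Waiting before treatment is part of the design. Footnote 1 to the inclusion criteria says: "The study will also include HCV positive patients who do not receive treatment either due to non-priority of treatment or presence of clinical contraindications". It adds: "These patients may receive treatment at a later date". Section 6.VIII refers to a yearly eligibility assessment. CRF2 item 272 (Appendix 2) has a waiting-list code. Table 1 bars treatment, with one exception, in the first three months of a new ART regimen.

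On calendar time, section 6.VII (Participant's recruitment) says: "During 2015 confirmation of active HCV infection was commenced within the program". Table 4 (section 6.XII) places recruitment from May 2017 to May 2019 and follow-up to August 2019.

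Section 6.V names Fisher's exact or chi-squared tests, t-tests or Wilcoxon tests, and unspecified univariate and multivariate models. It names no person-time, landmark or time-varying method.

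**The concern.** The two mortality groups are defined by an event that happens after the clock starts. To count as an initiator, a patient must first survive the wait. A patient who dies waiting is counted as without initiation. The initiators' waiting time is free of deaths by definition (immortal time), and any rate that includes it in their denominator is too low. The matching rate in the other group is too high, because it keeps the deaths during waiting but loses the waiting time of those who survived to start.

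A second, separate problem is length of follow-up. Initiators leave at SVR12, while patients never treated stay until death, exit or study end. A crude proportion dead therefore covers a much shorter period in the treated group.

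Both push the same way. Two figures printed next to each other would suggest that treatment protects against death even if it had no effect on death at all.

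**Working it through.** **The plan's own figures.** The protocol gives no death rate, waiting time or share treated. Its one related figure, the expected cohort size, reproduces: 1600 × 0.27 × 0.80 = 345.6, stated as 345.

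**Inputs from the protocol.** Recruitment lasts 2 years and follow-up ends about 2.25 years after the first inclusion (Table 4). Regimens last 12 or 24 weeks (Tables 2 and 3), so SVR12 falls 12 + 12 = 24 or 24 + 12 = 36 weeks after starting.

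**Assumptions.** Everyone has the same constant death rate, 2 to 5 per 100 person-years. Entry is uniform, and the wait to treatment is exponential. Other exits are ignored.

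**Unequal follow-up alone.** An initiator is followed for 24/52 = 0.46 or 36/52 = 0.69 years after starting. With an assumed 70/30 mix of 12- and 24-week regimens, that is 0.7 × 0.46 + 0.3 × 0.69 = 0.53 years. A never-treated patient is followed on average for (0.25 + 2.25)/2 = 1.25 years. With equal rates, the ratio of proportions dead is then roughly 0.53/1.25 = 0.42 before any immortal time is considered. Simulation with the mean wait cut to two weeks, which nearly removes immortal time, gives 0.37.

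**Immortal time in rates.** If a share *s* of the initiators' person-time is waiting time, their rate counted from confirmation is the true rate × (1 − *s*). With a true rate of 5 per 100 person-years and 12-week regimens, simulation gives:

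| Mean wait | Never treatable | *s* | 5 × (1 − *s*) | Simulated rate, treated / untreated | Rate ratio | Ratio of proportions dead | Rate ratio after splitting time |
|---|---|---|---|---|---|---|---|
| 1 month | 40% | 0.159 | 4.21 | 4.21 / 5.52 | 0.76 | 0.33 | 1.00 |
| 3 months | 20% | 0.348 | 3.26 | 3.26 / 8.20 | 0.40 | 0.24 | 1.00 |
| 6 months | 20% | 0.475 | 2.63 | 2.66 / 8.79 | 0.30 | 0.24 | 1.01 |
| 12 months | 20% | 0.565 | 2.18 | 2.17 / 7.76 | 0.28 | 0.25 | 0.99 |

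If all regimens last 24 weeks, the rate ratios for the same rows are 0.80, 0.44, 0.35 and 0.33, and the ratios of proportions are 0.47, 0.33, 0.33 and 0.35. A death rate of 2 per 100 person-years changes the ratios little.

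**Range.** For mean waits from two weeks to 12 months and 60% to 90% treatable, the rate ratio runs from about 0.24 to 0.89 and the ratio of proportions is about 0.2 to 0.4 (0.47 in the 24-week, one-month case above). Every scenario fell below 1. Splitting person-time at treatment start returned about 1.0 throughout.

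**The case against.** The strongest reply is that this endpoint is descriptive. Section 4 has no objective comparing survival by treatment, section 6.VIII states no ratio or test for mortality, and the two-group tests in section 6.V are generic. The window in section 6.I is written for assessing treatment effectiveness and does not expressly set time zero for initiators. Starting their clock at the first prescription, which section 6.V uses to define the ITT population, would give a correct treated rate, and an analysis plan not shown here could specify that. Much of this stands, and it limits the point to how two descriptive figures are built and presented. It does not remove it. The endpoint pairs the two groups, and the only clock stated starts at confirmation. Even with the treated clock moved, the untreated figure still depends on where waiting time is counted.

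A reader might infer more than the documents support:

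- **That the low ratio of proportions is an immortal-time effect.** It is mostly unequal follow-up, as the two-week-wait check shows. The proportion dead among initiators is the same wherever the clock starts.
- **That overall mortality is understated.** This holds only for a rate that counts time before consent, and it matters only for patients confirmed before recruitment opened. Section 6.IV invites patients when viral-load results become available. A proportion dead among those included is unaffected. The size of any dilution cannot be derived from the protocol.
- **That splitting person-time yields the effect of treatment on death.** It returns 1.0 here because the simulation gives everyone the same hazard. Table 1 bars from treatment patients with hepatocarcinoma, advanced or terminal disease, or uncontrolled infections, so a split ratio stays confounded by eligibility.

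**Conclusion.** The point holds as a fault in how a descriptive secondary endpoint is constructed. Under equal death rates, ever/never grouping on the stated clock always favours the treated group. The direction follows from the definitions. The size does not: about 0.24 to 0.89 for rates from confirmation and about 0.2 to 0.4 for crude proportions, both on assumed waits, treatable shares, death rates and regimen mix. With short waits the bias in the rates is modest, while the bias in the proportions remains. The protocol does not plan a mortality comparison, so the harm arises when the two figures are read together. The primary endpoint, SVR12 among patients who initiated treatment, is not affected. The change is worth making because it is cheap and the stated grouping has no advantage over it.

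**What to change.** Reword the mortality endpoint in section 6.VIII along these lines:

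- Report deaths per 100 person-years, overall and by current treatment status.
- Count time before the first HCV prescription as untreated and time from that prescription to SVR12 or exit as treated, so that one patient can contribute to both.
- Start counting at study entry (consent), because survival from viral-load confirmation to consent is guaranteed for patients confirmed before recruitment opened.
- Do not present crude proportions dead by ever-treated status side by side.
- State that any treated/untreated contrast is descriptive and remains confounded by the treatment eligibility criteria in Table 1.

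The analysis cost is one person-time split. Treatment start can be taken from the CRF2 consultation date with item 272. The sponsor must confirm that the dates of consent and death are captured: the pages shown record consent as Yes/No/DK (question 21, section 6.VI) and death as a reason for end of follow-up with no visible date (CRF2 item 290). If either date is missing, a field has to be added or the date taken from source records.
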